1.2.2 Secondary estimand(s)

There are no secondary estimands specified for this study.

2 Statistical methods

2.1 Data analysis general information

The statistical analysis outlined in this SAP will be performed by [REDACTED], a Novartis-designated Contract Research Organization (CRO), using SAS® version 9.4 or higher.

For continuous variables, descriptive statistics will include number of participants (n), mean, standard deviation, minimum, maximum, median and 25th and 75th percentiles. For categorical variables, frequency counts and percentages will be reported. Where appropriate, 2-sided 95% confidence intervals (CIs) for point estimates of the mean or proportion will be provided.

Unless otherwise stated, all data summaries will be presented by **cohort group** (see below) and on all participants in the respective analysis set.

- Cohort 1
- Cohorts 2 and 4 combined
- Cohorts 3 and 5 combined
- Cohort 6

All data will be listed appropriately.

2.1.1 General definitions

Treatment of interest

The treatment of interest will refer to the administration of a COVID-19 mRNA vaccine (either Pfizer or Moderna) to participants in each of the 6 cohorts. Participants will obtain a COVID-19 mRNA vaccine from their HCP (private insurance) or appropriate federal, state or local program.

Additional treatment

- Ofatumumab provided by Novartis in an auto-injector containing 20 mg s.c. ofatumumab (20 mg/0.4ml) for s.c. administration to participants in **Cohort 1** as per the assessment schedule.
- Commercially prescribed ofatumumab treatment for participants in **Cohort 2** as per their current dosing schedule.

- Commercially prescribed interferon or glatiramer acetate treatment for participants in **Cohort 3** as per their current dosing schedule.
- Commercially prescribed ofatumumab treatment for participants in **Cohort 4** as per their current dosing schedule.
- Commercially prescribed interferon or glatiramer acetate treatment for participants in **Cohort 5** as per their current dosing schedule.
- Commercially prescribed ofatumumab treatment for participants in **Cohort 6** as per their current dosing schedule

Study day, onset day, and event duration

The **study day** of an assessment will be derived relative to the date of Visit 2 (Study Day 1), primarily for use in the derivation of analysis visits using visit windows (see [Section 2.4.1.1](#)).

For data including but not limited to adverse events, medications, medical history, non-drug therapies/procedures and MS relapses, the **onset day** will be derived relative to the date of Visit 1 (Screening) as described below.

For event dates on or after the date of Visit 1, the day of the event will be calculated as follows:

- (date of event – date of Visit 1) + 1

For event dates prior to the date of Visit 1, the day of the event will be calculated as follows:

- (date of event – date of Visit 1)

The **duration of an event** in days will be calculated as follows:

- (event end date – event start date) + 1

Screening

Screening refers to any procedures (e.g., checking inclusion and exclusion criteria) performed prior to Visit 2 (Study Day 1) unless otherwise specified. Per protocol, participant informed consent must be obtained prior to performing any study related activity. The date of signing of informed consent is the start date of the screening period. Any assessment obtained during the screening period will be labelled as a screening assessment.

Pre-vaccination

Unless otherwise specified, pre-vaccination is the last non-missing assessment (including unscheduled assessments) obtained prior to the first dose of the COVID-19 vaccine. Pre-vaccination is only applicable to Cohorts 1, 2 and 3. All assessments obtained after the first dose of the COVID-19 vaccine are considered post-vaccination assessments unless otherwise specified.

Nominal visits

Nominal visits are defined as all scheduled visits as per the clinical study protocol including the EOS visit. The definition of nominal visit excludes unscheduled visits.

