### **Special guidance regarding the scheduling of visits for Cohorts 1, 2 and 3**

- The study site will need to perform Vaccine Status Check-ins (make remote contact with participant) to confirm when the 1st and 2nd COVID-19 vaccinations are scheduled in order to schedule Visit 4.
- The date of the 2nd COVID-19 vaccine dose will determine the date of Visit 4 and all other remaining study visits.
- Visits 2 and 3 should always occur prior to administration of the mRNA vaccine.
- The Visit 4 lab samples should be collected 14 days after a participant has received their 2nd COVID-19 vaccine dose.

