2.4.1.1 Visit windows

Visit windows will be used for data that are summarized by visit; they are based on the study evaluation schedule and comprise a set of days around the nominal visit day. When visit windows are used, all visits, including unscheduled visits, will be re-aligned (i.e., they will be mapped into one of the visit windows). In the case of major deviations from the visit schedule, or due to unscheduled visits, several assessments for a participant may fall in a particular visit window (either scheduled or unscheduled). Approaches for handling multiple assessments in a visit window are outlined below.

The following steps are used to determine the cut-offs for visit windows:

- The visit window associated with the previous assessment ends prior to the middle point; the visit window associated with the latter assessment begins after the middle point. In case the middle point is an exact study day, it will belong to the previous assessment.
- The visit window of the first post-vaccination assessment starts the day after the second dose of the COVID-19 vaccine for Cohorts 1 – 5, and the day after the COVID-19 vaccine booster for Cohort 6, unless otherwise specified.

Tables 2 – 10 provide visit windows for applicable parameters.

Table 2**Cohort 1 visit windows for SARS-CoV-2 qualitative antibody / CD19+ B cells / T cell**

Analysis visit	Nominal time point	Scheduled visit day (target study day)	Visit window (study days)
Pfizer vaccine:			
Pre-vaccination	Day 1	1	≤1
14 days post-vaccination	Day 36	36	(vaccine day + 1) to 64
70 days post-vaccination	Day 92	92	65 to 147
180 days post-vaccination	Day 202	202	148 to 247
270 days post-vaccination	Day 292	292	248 to 337
360 days post-vaccination	Day 382	382	≥338
Moderna vaccine:			
Pre-vaccination	Day 1	1	≤1
14 days post-vaccination	Day 43	43	(vaccine day + 1) to 71
70 days post-vaccination	Day 99	99	72 to 154
180 days post-vaccination	Day 209	209	155 to 254
270 days post-vaccination	Day 299	299	255 to 344
360 days post-vaccination	Day 389	389	≥345

Note:

- Pre-vaccination and study day are derived as outlined in [Section 2.1.1](#).
- Vaccine day is the study day of the second dose of the COVID-19 vaccine.
- Assessments performed between the first and second doses of the COVID-19 vaccine are not assigned an analysis visit.

Table 3**Cohort 1 visit windows for serum immunoglobulin (IgG, IgM)**

Analysis visit	Nominal time point	Scheduled visit day (target study day)	Visit window (study days)

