- Assessments performed between the first and second doses of the COVID-19 vaccine are not assigned an analysis visit.

Table 8**Cohorts 4, 5 and 6 visit windows for SARS-CoV-2 qualitative antibody / CD19+ B cells (Cohorts 4 and 6 only) / T cell**

Analysis visit	Nominal time point	Scheduled visit day (target study day)	Visit window (study days)
Pfizer vaccine:			
14 days post-vaccination	Day 1	1	(vaccine day + 1) to 1
180 days post-vaccination	Day 202	202	2 to 247
270 days post-vaccination	Day 292	292	248 to 337
360 days post-vaccination	Day 382	382	≥338
Moderna vaccine:			
14 days post-vaccination	Day 1	1	(vaccine day + 1) to 1
180 days post-vaccination	Day 209	209	2 to 254
270 days post-vaccination	Day 299	299	255 to 344
360 days post-vaccination	Day 389	389	≥345

Note:

[figure not shown]
- Study day is derived as outlined in [Section 2.1.1](#).
- Vaccine day is the study day of the second dose of the COVID-19 vaccine for Cohorts 4 and 5, and the study day of the COVID-19 vaccine booster for Cohort 6.

Table 9 **Cohorts 4, 5 and 6 visit windows for serum immunoglobulin (IgG, IgM)**

Analysis visit	Nominal time point	Scheduled visit day (target study day)	Visit window (study days)
Pfizer vaccine:			
14 days post-vaccination	Day 1	1	(vaccine day + 1) to 1
180 days post-vaccination	Day 202	202	2 to 292
360 days post-vaccination	Day 382	382	≥293
Moderna vaccine:			
14 days post-vaccination	Day 1	1	(vaccine day + 1) to 1
180 days post-vaccination	Day 209	209	2 to 299
360 days post-vaccination	Day 389	389	≥300

Note:

- Study day is derived as outlined in [Section 2.1.1](#).
- Vaccine day is the study day of the second dose of the COVID-19 vaccine for Cohorts 4 and 5, and the study day of the COVID-19 vaccine booster for Cohort 6.

Multiple assessments

When there are multiple assessments in a particular visit window, the rules outlined below are applied to select one value “representing” the participant in summary statistics for that visit window. All assessments will be displayed in listings.

- **Pre-vaccination (only applicable to Cohorts 1, 2 and 3):** Pre-vaccination is derived as outlined in [Section 2.1.1](#). In situations where the same assessment is performed more than once on Study Day 1 the repeated assessment will be used.
- **Post-vaccination:** For post-vaccination visit windows, the following rules apply (unless otherwise specified):

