2.5.3 Handling of intercurrent events

Non-response imputation (NRI) approach will be applied to missing post-vaccination antibody assay regardless of intercurrent events.

NRI is a conservative imputation method for dichotomous variables. NRI assumes that a participant is a treatment failure if the participant discontinues the study prematurely. Hence, for missing data the primary endpoint will be imputed as “No”. Refer to [Section 5.1.3.3](#).

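### Cohort 1-3 visits are scheduled from the second vaccine dose, but the SAP closes their analysis windows on fixed days counted from Visit 2, so a long enough vaccination delay mislabels on-protocol samples

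*SAP*

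**What the plan says.** **Protocol.** Participants obtain the vaccine from outside providers. The scheduling guidance for Cohorts 1-3 in Section 8 says that the date of the second "COVID-19 vaccine dose will determine the date of Visit 4 and all other remaining study visits". It adds: "The Visit 4 lab samples should be collected 14 days after a participant has received their" second dose. Visit 2 precedes vaccination. We found no maximum interval from Visit 2 to dose 1 or from dose 1 to dose 2. Section 9.1.2 removes participants who do not complete the two-dose course, but gives no deadline.

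**SAP.** Section 2.1.1 says that study day "will be derived relative to the date of Visit 2 (Study Day 1), primarily for use in the derivation of analysis visits". Section 2.4.1.1 maps all visits, scheduled or not, to windows by study day. It places cut-offs midway between target days: "The visit window associated with the previous assessment ends prior to the middle point". The first post-vaccination window opens the day after dose 2 in Cohorts 1-3. For the qualitative antibody in Cohort 1 (Pfizer), Table 2 gives it as "vaccine day + 1) to 64". The Moderna window ends on Day 71. Table 5 ends the same window for Cohorts 2-3 on Day 119 (Pfizer) or 126 (Moderna).

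**Missing data.** SAP 2.5.3 and 2.5.4 apply non-responder imputation to a missing post-vaccination assay. In the words of 2.5.3, "Hence, for missing data the primary endpoint will be imputed as" a no. Section 2.5.3 then refers to 5.1.3.3, which describes a non-responder as someone with no valid assessment after both doses. SAP 1.1 names Visit 4 as the primary analysis time point for these cohorts.

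**The concern.** The primary window has two anchors. Its lower edge moves with dose 2 and its upper edge does not. A delay in vaccination, including any lag between Visit 2 and dose 1, therefore shortens the window and eventually closes it before it opens. A sample taken on the day the protocol asks for, and meeting the endpoint definition of at least 14 days after the full course, can then be filed as 70 or 180 days post-vaccination. Later visits drift in the same way, which affects the sustained-response endpoint.

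The error would follow vaccination logistics, not immune response. It would arise sooner in Cohort 1, whose primary window is the shorter. If a misfiled sample also counts as missing, the response rate falls for a reason unrelated to the vaccine or to ofatumumab.

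**Working it through.** **1. Reproduce the SAP's cut-offs.** The midpoint rule applied to the target days gives:

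- Cohort 1: (36 + 92)/2 = 64 (Pfizer); (43 + 99)/2 = 71 (Moderna).
- Cohorts 2-3: (36 + 202)/2 = 119 (Pfizer); (43 + 209)/2 = 126 (Moderna).

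These match Tables 2 and 5, as do the later cut-offs (147/247/337 and 154/254/344 in Cohort 1; 247/337 and 254/344 in Cohorts 2-3).

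**2. Delay at which Visit 4 leaves the primary window.** Planned dose 2 is Day 22 (Pfizer) or Day 29 (Moderna). With Visit 4 at dose 2 + 14, the smallest delay that puts it outside is: upper edge − 14 − planned dose-2 day + 1. The window cannot open once dose 2 falls on or after its upper edge.

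| Group | Upper edge | First dose-2 day outside | Delay | Window empty from delay |
|---|---|---|---|---|
| Cohort 1, Pfizer | 64 | 51 | 64 − 14 − 22 + 1 = 29 | 64 − 22 = 42 |
| Cohort 1, Moderna | 71 | 58 | 71 − 14 − 29 + 1 = 29 | 71 − 29 = 42 |
| Cohorts 2-3, Pfizer | 119 | 106 | 119 − 14 − 22 + 1 = 84 | 119 − 22 = 97 |
| Cohorts 2-3, Moderna | 126 | 113 | 126 − 14 − 29 + 1 = 84 | 126 − 29 = 97 |

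If Visit 4 is drawn 3 days late, within its allowed window, the thresholds fall to 26 and 81 days.

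**3. Later visits.** Let d be the delay in days.

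- 180-day visit: 202 + d > 247 from d = 46.
- 270-day visit: 292 + d > 337 from d = 46.
- The Moderna days are all 7 later, so the thresholds are the same.

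**4. Visits sharing a window.**

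- In Cohort 1, Visit 4 (36 + d) and Visit 8 (92 + d) both lie in Days 65-147 for d = 29 to 55.
- In all three cohorts, the 270- and 360-day visits both lie in the 360-day window from d = 46 (292 + 46 = 338).

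SAP 2.4.1.1 keeps the worst result for a categorical variable. For a category based on a continuous variable, it uses the analysis visit assigned to the continuous value, chosen as closest to target. Neither rule repairs the label. At d = 29, Visit 4 falls on Day 65 (27 days from the Day 92 target) and Visit 8 on Day 121 (29 days from it). The closest-to-target rule would therefore report the 14-day sample as the 70-day result.

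**5. Size if a misfiled responder is scored a non-responder.**

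- n = 22: 1/22 = 4.5 points. For example, 18/22 = 81.8% (exact 95% CI 59.7-94.8) becomes 17/22 = 77.3% (54.6-92.2).
- n = 20: 1/20 = 5.0 points. For example, 16/20 = 80% (56.3-94.3) becomes 15/20 = 75% (50.9-91.3).

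The documents give no delays. On an assumed range of 0 to 3 affected responders in a group, the loss is 0 to 15 points at n = 20 (3/20) and 0 to 13.6 points at n = 22 (3/22).

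**6. The same rule counted from dose 2.** Targets are 14, 70, 180, 270 and 360 days in Cohort 1, without 70 in Cohorts 2-3.

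- Cohort 1: (14 + 70)/2 = 42; (70 + 180)/2 = 125; (180 + 270)/2 = 225; (270 + 360)/2 = 315.
- Cohorts 2-3: (14 + 180)/2 = 97; then 225 and 315.

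On the planned schedule these return the present primary edges: 22 + 42 = 64, 29 + 42 = 71, 22 + 97 = 119, 29 + 97 = 126. Visit 4 at dose 2 + 14 always stays inside.

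**The case against.** The strongest reply is that nobody need be scored a non-responder. SAP 1.1 identifies the primary time point by visit. The endpoint has no upper time limit. Section 5.1.3.3 reserves imputation for participants without a valid assessment after both doses, and a participant with a Visit 4 result has one. This stands against certainty but does not settle the matter. Table 2 expressly covers the qualitative antibody, all visits are re-aligned, and the SAP never says which record feeds the primary analysis. Under 5.1.3.3 the participant is not imputed but still has no record in the primary window, and no rule covers that case.

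Second, the windows already absorb 28 days of slippage in Cohort 1 and 83 in Cohorts 2-3, and the protocol asks for visits as close to schedule as possible. The SAP's revision history also says that the windows were updated after a review of data. So this may be a rare event or none at all. That stands for frequency, but it does not remove the conflict between the two anchors.

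Third, the worst-result rule may not govern if the qualitative call derives from a quantitative value. That also stands, although the time-point label is wrong either way.

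A reader might extend the point to Cohorts 4-6, where Table 8 closes the first window on Day 1 ("vaccine day + 1) to 1") and not at a midpoint. The documents do not support the same change there. These cohorts have no pending second dose, and no repeat of the Visit 2 draw is scheduled. A midpoint edge, (1 + 202)/2 = 101.5 or (1 + 209)/2 = 105, would let later unscheduled draws, including some after an on-study booster, compete with the Visit 2 result.

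**Conclusion.** The mismatch is real and should be corrected. As written, the SAP relabels an on-protocol Visit 4 sample from a delay of 29 days in Cohort 1 and 84 days in Cohorts 2-3. It relabels the 180- and 270-day visits from 46 days in all three cohorts. These thresholds assume that later visits keep their planned distance from dose 2, as the protocol directs. Immune conversion is largely spared, because SAP 2.6.1 accepts any assessment at least 14 days after the full course.

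Two stronger inferences are tempting and not supported. One is that any late second dose does harm; it takes about a month in Cohort 1 and about twelve weeks in Cohorts 2-3 to affect the primary window. The other is that an affected participant is necessarily a non-responder. That follows only if 2.5.3-2.5.4 are applied to the re-aligned record. The loss of 4.5 or 5.0 points per affected responder is therefore conditional, and the number affected is unknown and may be zero.

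**What to change.** 1. For Cohorts 1-3, define post-vaccination windows and target days in days since dose 2. Qualitative antibody cut-offs become 42, 125, 225 and 315 in Cohort 1, and 97, 225 and 315 in Cohorts 2-3.
2. Re-base the serum immunoglobulin windows (Tables 3 and 6) in the same way. Their last cut-off becomes (180 + 360)/2 = 270, which matches the present edges on schedule (22 + 270 = 292; 29 + 270 = 299).
3. State whether nominal Visit 4 or the windowed record feeds the primary analysis.
4. Align 2.5.3-2.5.4 with 5.1.3.3, and say whether the same reading holds for the secondary time points in 2.6.3-2.6.4.
5. Leave Table 8 as it is.

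The cost is a change to SAP tables and programming before database lock, with no new data. For participants vaccinated on schedule the window edges do not move. For those vaccinated late, the edges move with dose 2, so unscheduled draws near an edge may change label, which is the intended effect.

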2.2 Analysis sets

The Safety Analysis Set (SAF) comprises all participants who signed informed consent and met all entry criteria.

Unless otherwise specified the SAF will be used for all summary tables and listings.

2.2.1 Subgroup of interest

There is no subgroup analysis planned for this study.

2.3 Patient disposition, demographics and other baseline characteristics

2.3.1 Patient disposition

Participant disposition will be summarized for the following disposition events using all screened participants:

- Screening
- Treatment
- End of study

Participants who have discontinued from the study will be listed as appropriate along with the primary reason for discontinuation.

The number and percentage of screen failures and the reason for screen failure will be presented for all screened participants.

For each protocol deviation, the number and percentage of participants for whom the deviation applies will be summarized by cohort group.

2.3.2 Demographics and other baseline characteristics

The following demographic variables will be summarized descriptively by cohort group:

Continuous variables

- Age (years)

Categorical variables

- Sex (Male, Female)
- Ethnicity (Hispanic or Latino, Not Hispanic or Latino, Not reported, Unknown)
- Race (White, Black or African American, Asian [Chinese, Indian, Japanese, Korean, Vietnamese], Native Hawaiian or Other Pacific Islander, American Indian or Alaska Native, Multiple)

2.3.3 MS history

The number and percentage of participants with a relapse in the last 90 days prior to screening will be presented by cohort group.

The following variable will be summarized descriptively as a continuous variable by cohort group:

- Time (days) from onset of most recent relapse (in the last 90 days prior to screening) to Visit 1 (Screening), in participants with a relapse in the last 90 days prior to screening

2.3.4 Medical history

Medical history will be coded using the Medical Dictionary for Regulatory Activities (MedDRA) terminology. The MedDRA version used for reporting the study will be indicated in a footnote on relevant outputs.

Medical history will be summarized with frequency counts and percentages by cohort group, primary system organ class (SOC) and preferred term (PT). Tables will show the overall number and percentage of participants with at least one reported medical history event in a particular primary SOC and at least one reported medical history event in a particular PT.

2.4 Treatments (study treatment, rescue medication, concomitant therapies, compliance)

2.4.1 Study treatment / compliance

Participants in all cohorts must intend to receive or have received both doses of a COVID-19 mRNA vaccine.

The following variables will be summarized descriptively as continuous variables by cohort group unless otherwise specified:

- Time (days) from first dose of ofatumumab to last dose of ofatumumab for Cohort 1 participants
- Time (days) from first dose of earliest MS DMT to:
 - first dose of COVID-19 vaccine
 - primary analysis time point (see [Section 1.1](#))
- Time (days) from first dose of most recent MS DMT to:
 - first dose of COVID-19 vaccine
 - primary analysis time point (see [Section 1.1](#))

MS treatment compliance will be listed by individual cohort and participant.

Study duration

Study duration in days will be calculated as [(date of last contact/EOS – date of Visit 1) + 1] and summarized descriptively as a continuous variable by cohort group.

2.4.1.1 Visit windows

Visit windows will be used for data that are summarized by visit; they are based on the study evaluation schedule and comprise a set of days around the nominal visit day. When visit windows are used, all visits, including unscheduled visits, will be re-aligned (i.e., they will be mapped into one of the visit windows). In the case of major deviations from the visit schedule, or due to unscheduled visits, several assessments for a participant may fall in a particular visit window (either scheduled or unscheduled). Approaches for handling multiple assessments in a visit window are outlined below.

The following steps are used to determine the cut-offs for visit windows:

- The visit window associated with the previous assessment ends prior to the middle point; the visit window associated with the latter assessment begins after the middle point. In case the middle point is an exact study day, it will belong to the previous assessment.
- The visit window of the first post-vaccination assessment starts the day after the second dose of the COVID-19 vaccine for Cohorts 1 – 5, and the day after the COVID-19 vaccine booster for Cohort 6, unless otherwise specified.

Tables 2 – 10 provide visit windows for applicable parameters.

Table 2**Cohort 1 visit windows for SARS-CoV-2 qualitative antibody / CD19+ B cells / T cell**

Analysis visit	Nominal time point	Scheduled visit day (target study day)	Visit window (study days)
Pfizer vaccine:			
Pre-vaccination	Day 1	1	≤1
14 days post-vaccination	Day 36	36	(vaccine day + 1) to 64
70 days post-vaccination	Day 92	92	65 to 147
180 days post-vaccination	Day 202	202	148 to 247
270 days post-vaccination	Day 292	292	248 to 337
360 days post-vaccination	Day 382	382	≥338
Moderna vaccine:			
Pre-vaccination	Day 1	1	≤1
14 days post-vaccination	Day 43	43	(vaccine day + 1) to 71
70 days post-vaccination	Day 99	99	72 to 154
180 days post-vaccination	Day 209	209	155 to 254
270 days post-vaccination	Day 299	299	255 to 344
360 days post-vaccination	Day 389	389	≥345

Note:

- Pre-vaccination and study day are derived as outlined in [Section 2.1.1](#).
- Vaccine day is the study day of the second dose of the COVID-19 vaccine.
- Assessments performed between the first and second doses of the COVID-19 vaccine are not assigned an analysis visit.

Table 3**Cohort 1 visit windows for serum immunoglobulin (IgG, IgM)**

Analysis visit	Nominal time point	Scheduled visit day (target study day)	Visit window (study days)
Pfizer vaccine:			
Pre-vaccination	Day 1	1	≤1
14 days post-vaccination	Day 36	36	(vaccine day + 1) to 64
70 days post-vaccination	Day 92	92	65 to 147
180 days post-vaccination	Day 202	202	148 to 292
360 days post-vaccination	Day 382	382	≥293
Moderna vaccine:			
Pre-vaccination	Day 1	1	≤1
14 days post-vaccination	Day 43	43	(vaccine day + 1) to 71
70 days post-vaccination	Day 99	99	72 to 154
180 days post-vaccination	Day 209	209	155 to 299
360 days post-vaccination	Day 389	389	≥300

Note:

- Pre-vaccination and study day are derived as outlined in [Section 2.1.1](#).
- Vaccine day is the study day of the second dose of the COVID-19 vaccine.
- Assessments performed between the first and second doses of the COVID-19 vaccine are not assigned an analysis visit.

[figure not shown]

Table 5**Cohorts 2 and 3 visit windows for SARS-CoV-2 qualitative antibody / CD19+ B cells (Cohort 2 only) / T cell**

Analysis visit	Nominal time point	Scheduled visit day (target study day)	Visit window (study days)
Pfizer vaccine:			
Pre-vaccination	Day 1	1	≤1
14 days post-vaccination	Day 36	36	(vaccine day + 1) to 119
180 days post-vaccination	Day 202	202	120 to 247
270 days post-vaccination	Day 292	292	248 to 337
360 days post-vaccination	Day 382	382	≥338
Moderna vaccine:			
Pre-vaccination	Day 1	1	≤1
14 days post-vaccination	Day 43	43	(vaccine day + 1) to 126
180 days post-vaccination	Day 209	209	127 to 254
270 days post-vaccination	Day 299	299	255 to 344
360 days post-vaccination	Day 389	389	≥345

Note:

- Pre-vaccination and study day are derived as outlined in [Section 2.1.1](#).
- Vaccine day is the study day of the second dose of the COVID-19 vaccine.
- Assessments performed between the first and second doses of the COVID-19 vaccine are not assigned an analysis visit.

Table 6**Cohorts 2 and 3 visit windows for serum immunoglobulin (IgG, IgM)**

Analysis visit	Nominal time point	Scheduled visit day (target study day)	Visit window (study days)
Pfizer vaccine:			
Pre-vaccination	Day 1	1	≤1
180 days post-vaccination	Day 202	202	(vaccine day + 1) to 292
360 days post-vaccination	Day 382	382	≥293
Moderna vaccine:			
Pre-vaccination	Day 1	1	≤1
180 days post-vaccination	Day 209	209	(vaccine day + 1) to 299
360 days post-vaccination	Day 389	389	≥300

Note:

- Pre-vaccination and study day are derived as outlined in [Section 2.1.1](#).
- Vaccine day is the study day of the second dose of the COVID-19 vaccine.
- Assessments performed between the first and second doses of the COVID-19 vaccine are not assigned an analysis visit.

Table 8**Cohorts 4, 5 and 6 visit windows for SARS-CoV-2 qualitative antibody / CD19+ B cells (Cohorts 4 and 6 only) / T cell**

Analysis visit	Nominal time point	Scheduled visit day (target study day)	Visit window (study days)
Pfizer vaccine:			
14 days post-vaccination	Day 1	1	(vaccine day + 1) to 1
180 days post-vaccination	Day 202	202	2 to 247
270 days post-vaccination	Day 292	292	248 to 337
360 days post-vaccination	Day 382	382	≥338
Moderna vaccine:			
14 days post-vaccination	Day 1	1	(vaccine day + 1) to 1
180 days post-vaccination	Day 209	209	2 to 254
270 days post-vaccination	Day 299	299	255 to 344
360 days post-vaccination	Day 389	389	≥345

Note:

[figure not shown]
- Study day is derived as outlined in [Section 2.1.1](#).
- Vaccine day is the study day of the second dose of the COVID-19 vaccine for Cohorts 4 and 5, and the study day of the COVID-19 vaccine booster for Cohort 6.

Table 9 **Cohorts 4, 5 and 6 visit windows for serum immunoglobulin (IgG, IgM)**

Analysis visit	Nominal time point	Scheduled visit day (target study day)	Visit window (study days)
Pfizer vaccine:			
14 days post-vaccination	Day 1	1	(vaccine day + 1) to 1
180 days post-vaccination	Day 202	202	2 to 292
360 days post-vaccination	Day 382	382	≥293
Moderna vaccine:			
14 days post-vaccination	Day 1	1	(vaccine day + 1) to 1
180 days post-vaccination	Day 209	209	2 to 299
360 days post-vaccination	Day 389	389	≥300

Note:

- Study day is derived as outlined in [Section 2.1.1](#).
- Vaccine day is the study day of the second dose of the COVID-19 vaccine for Cohorts 4 and 5, and the study day of the COVID-19 vaccine booster for Cohort 6.

Multiple assessments

When there are multiple assessments in a particular visit window, the rules outlined below are applied to select one value “representing” the participant in summary statistics for that visit window. All assessments will be displayed in listings.

- **Pre-vaccination (only applicable to Cohorts 1, 2 and 3):** Pre-vaccination is derived as outlined in [Section 2.1.1](#). In situations where the same assessment is performed more than once on Study Day 1 the repeated assessment will be used.
- **Post-vaccination:** For post-vaccination visit windows, the following rules apply (unless otherwise specified):
 - For *continuous variables*, the assessment with the study day that is closest to the target study day is selected. If two assessments are equidistant from the target study

day, the earlier assessment is selected (if one of the two equidistant assessments is an unscheduled assessment, it should be excluded from consideration).

- For *categorical variables*, the assessment with the worst result is selected.

If categorical variables are based on continuous variables, the analysis visit will be assigned to the continuous variable, and this analysis visit will be used for the derived categorical variable.

In situations where the same assessment is performed more than once on the same date the repeated assessment will be used.

